7.1 Subject Identification

Subjects appropriate for this trial will be identified by the investigator (or designee) who will make a preliminary determination of the subject's eligibility for the trial in accordance with the provisions of the study protocol.

Documentation of the personally signed and dated Informed Consent Form (ICF) for each subject is required before initiating the screening process. After written ICF has been obtained and eligibility to participate established, investigative site personnel will obtain the subject's identification number and study drug assignment as appropriate.

7.2 Study Start and End of Study Definitions

The start of the study is defined as the date the first subject, who is subsequently enrolled, signs an ICF. The point of enrolment occurs at the time of subject number allocation. The end of study is defined as the date of the last subject's last assessment.

7.3 Description of Assessments

7.3.1 Laboratory Assessments

All protocol required clinical laboratory assessments should be performed at the investigational site's local laboratory. All clinical laboratory results must be documented on the CRF and reference ranges and safety parameters must be provided for each laboratory used. The following assessments will be performed and evaluated during the study.

Table 10 Laboratory Assessments

Hematology	red blood cell counts (RBC), white blood cell counts (WBC), and differential counts (neutrophils (NE), lymphocytes (LY#), monocytes (MO#), eosinophils (EO#), and basophils (BA)), platelet count (PLT), hemoglobin (HGB), and hematocrit (HCT)
Coagulation Function	PT (Prothrombin Time), APTT (Partial Thromboplastin Time), INR (International Normalized Ratio), Thrombin time (TT) and fibrinogen (FIB)
Fasting Serum Biochemistry	ALT, AST (Aspartate Transaminase), GGT (Gamma-glutamyl Transpeptidase), TBIL (total bilirubin), DBIL (direct bilirubin), BUN (Urea Nitrogen) or urea, Cr (Creatinine), UA (uric acid), GLU (blood glucose), potassium, sodium, chlorine, calcium, phosphate, magnesium, TP (total protein), ALB (albumin), albumin/globulin ratio, LDH (Lactate Dehydrogenase), TBA (Total Bile Acid), TG (Triglyceride), CK (Creatine kinase), CK-MB (creatinine kinase isoenzyme) and ALP (Alkaline Phosphatase).

Pregnancy Test	serum β -Human Chorionic Gonadotropin (β -HCG). Lack of childbearing potential must be noted in the source documents, if applicable.
Urinalysis	specific gravity, pH, white blood cells, red blood cells, α 1 microglobulin, β macroglobulin, occult blood, proteins and glucose.
Infectious Disease Screening	HCV, HBV, HIV, syphilis, etc., but if the subject can present the test results done within 4 weeks prior to the administration, the screening can be exempted.

7.3.2 Medical History

Medical history, including details of illnesses and allergies, date(s) of onset, whether condition(s) is currently ongoing, and medication history (anti-tumor therapies), including nicotine and alcohol use, will be collected for all subjects during screening.

7.3.3 Physical Examination

A complete physical examination should include source documentation of general appearance, and following body systems: head, neck and thyroid; eyes, ears, nose, throat, mouth and tongue; chest; respiratory, cardiovascular; lymph nodes; abdomen; skin, hair, nails, musculoskeletal; neurological and mental status.

Height, and body weight will be collected at specified time points.

7.3.4 Vital Signs

Vital signs measurement includes respiratory rate, heart rate, body temperature and blood pressure. Heart rate and blood pressure will be first checked in the seat position and then in the standing position at every time point of the scheduled plan.

7.3.5 Electrocardiogram

Standard 12-lead ECG assessments will be performed, after resting in supine position for at least 5 min to assess heart rate, rhythm, and interval information such as PR, QRS, QT, QTc and so on. The Investigator will review the ECGs for any clinically significant abnormalities to ensure subject safety.

If a subject has possible cardiac-related symptoms, repeat ECGs will be obtained every 30 min \pm 3 min until the waveform reverts to its baseline appearance, or symptoms resolve, or are determined not to be cardiac-related. Participants with cardiac-related symptoms that are associated with ECG changes will be transferred to appropriate emergency department for further evaluation and treatment at the discretion of the Investigator.

7.3.6 Echocardiogram

Echocardiogram will be performed during the study and left ventricular ejection fraction (LVEF) was recorded.

7.3.7 ^{18}F -FES PET/CT

The patients underwent both ^{18}F -FES and ^{18}F -FDG PET/CT at screening period and C2D8 to monitor the detect in ER target occupation and inhibition. The detection interval between ^{18}F -FES and ^{18}F -FDG PET/CT was within 7 days.

All of the patients were requested to fast for more than 4 h prior to ^{18}F -FES PET/CT scans to eliminate the excretion of ^{18}F -FES from the hepatobiliary system and the gastrointestinal tract, which might interfere with image interpretation in the pelvic cavity.

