	
of $>38.3^{\circ}\text{C}$ (101°F) or a sustained temperature of $\geq 38^{\circ}\text{C}$ (100°F) for more than one hour;
 
• CTCAE Grade 3 thrombocytopenia ($\geq 25,000/\text{mm}^3$ and $<50,000/\text{mm}^3$) associated with bleeding; 
2. Non-hematological toxicity:
 
• Hy's law, defined as:
◇ AST or ALT > 3 x the upper limit of normal (ULN) AND◇ Total bilirubin > 2 x ULN AND◇ Alkaline phosphatase < 2 x ULN AND◇ No other reason for liver injury• ALT or AST >8x ULN, ALT or AST >5x ULN for more than 2 weeks, ALT or AST >3x ULN and (TBL >2x ULN or INR >1.5)
◇ For patients with hepatic metastases, AST or ALT > 8 x ULN or ALT or AST > 5 x ULN for ≥ 14 days• Grade > 3 non-hematologic toxicity with the exception of the following
◇ Grade 3+ fatigue ≥ 7 days regardless of baseline grade;◇ Grade 3 nausea and vomiting, lasting ≤ 2 days with optimal medical management;◇ Grade 3 diarrhea lasting ≤ 3 days with optimal medical management◇ $\geq 3+$ non-hematologic abnormalities should also include laboratory values that cause symptoms. 
MTD Evaluation period:
 
• Part A: FWD1802 single dose run-in period (C0:D1-D6 intake on D1, then off until D6) and 1st 28-day treatment cycle (C1:D1-D28), total of 34 days;• Part B: the 1st treatment cycle of FWD1802 in combination with palbociclib (C1:D1-D28)
--	---

Duration of treatment	Reiterated treatment cycles of 4 weeks until progression disease based on radiological evaluation, undue drug toxicity, withdrawal of consent or death, whichever occurs first.
PK/PD Sample	Please see Section 7.5.1 PK Samples and Section 7.3.7 18F-FES PET/CT.

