14. Tumor assessment: All patients will undergo MRI, chest, abdomen, pelvis and bone examination at baseline period, and subsequent imageological examination included the chest, abdomen, pelvis, and other metastatic sites, if any. The preferred imaging methodology is CT enhanced scan, and using the same imaging examination method and examination conditions before and after the same lesion (including scanning slice thickness, contrast agent, etc.). However, If patient has a contrast allergy or intolerance to contrast medium, a plain CT scan is allowed. During the treatment period, imageological examination and efficacy assessment should be repeated every 8 weeks (± 7 days) from C1D1 for the first 12 months, then every 12 weeks (± 7 days) thereafter until disease progression. Each imaging examination should be performed in accordance with the original imaging schedule, without adjustment due to dose delay. Tumor assessments will continue until disease progression and will not be interrupted due to discontinuation of the study treatment.

- CT/MRI examination in the screening period should be confirmed by the sponsor to be acceptable with the test results before the COD1 meeting the requirements (including the test results before the subject signs the informed consent form).
- Bone scan should be performed during the screening period. The bone scan during the screening period was performed by the sponsor to confirm the results of the research hospital within 42 days before the COD1 that could meet the research requirements (including the results of the examination before the subject signed the informed consent). Bone scan was performed only when there were clinical indications during the study period.
- The investigator may perform off-schedule imaging assessment at any time when disease progression is suspected. Subjects with a first CR or PR should be confirmed by imaging confirmation or the next efficacy evaluation after at least 4 weeks..

12. Using 18F-FES PET to monitor the detect in ER target occupation and inhibition.

Table 3 Schedule of Events in Part C Dose Expansion

Items	Screening ¹	Expansion			Follow-up		
		Cycle 1	Cycle 2	≥Cycle3	EOT ²	SFU ³	LTFU ⁴
Visit Day	D28~ D-1	D1	D 1	D1			
Evaluation Window (Days)		0	±3	±3	±7	±7	±7
Administrative Procedures							
Informed Consent	X						
Inclusion/Exclusion Criteria	X						
Demographics	X						
Medical history	X						
Concurrent diseases	X						
Clinical Procedures/Assessments							

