3.4 Exploratory endpoints

- The correlation between ER target inhibition by using [^{18}F]-fluorestradiol (FES) PET/CT and efficacy.
- Progression free survival (PFS) and Overall survival (OS).
- Other potential biomarker as needed.

4 Investigational Plan

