4.5 Definition of MTD

- The maximum tolerable dose (MTD) is defined as the highest dose level while the incidence of DLT is less than 33% in the dose escalation study during the DLT evaluation period.
- Six patients are required to establish the MTD. If only 3 patients have been evaluated in the previous dose level below the non-tolerated dose, the cohort should be expanded to 6 patients at the previous dose level below the non-tolerated dose. If DLT is not observed in the additional 3 patients, or 6 patients have been evaluated at the previous

dose level, the MTD will be confirmed at the previous dose level below the non-tolerated dose.

- If MTD is not established at the end of escalation, the maximum safety dose will be defined as the maximum administrated dose (MAD).
- The recommended dose for expansion(s) will be confirmed comprehensively based on the results of safety, tolerability, PK and PD. The RP2D should be a pharmacologically active dose and the dose should be selected by pooling and evaluating all available PK, PD, target engagement, efficacy, safety, and tolerability data to select the appropriate dose. There will need to be at least 6 patients at the recommended dose for expansion level(s) to evaluate the safety, PK, PD and tolerability. If the DLT does not occur during the DLT assessment period, the current highest dose level will not be considered as the basis of dose escalation and may be used as a reference to dose design and safety evaluation of the recommend dose.

Based on the safety data, a higher dose level beyond dose level 9 or an intermediate dose level can be explored as determined by the SMC.

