7.4.1 Screening Period (Day -28~Day -1) for All Subjects

After signing the ICF, a subject should undergo medical screening to assess whether he/she is eligible to participate in the study according to the inclusion criteria. The screening evaluation will be completed within 28 days prior to the first administration of the investigational drug.

Administrative Procedures:

- Informed Consent
- Inclusion/Exclusion Criteria
- Demographics
- Medical history
- Concurrent diseases

Clinical Procedures/Assessments:

- Weight
- Body height
- Physical examination
- vital signs

- ECOG Score
- 12-lead ECG
- Echocardiogram

Laboratory tests:

- Blood Chemistry
- Hematology
- Coagulation
- Urinalysis
- Virology: HBV, HCV, and HIV
- Pregnancy
- COVID-19

Efficacy Assessments:

- Tumor Assessment

Biomarker Exploration:

- ¹⁸F-FES PET/CT15

Other:

- Adverse events and concomitant medication;

The information above should be obtained from the source file. For test values outside the normal range (outliers), the investigator will assess whether to repeat the test.

The investigator will review patient's medical history at the time of screening period. The history includes all current active diseases and any other conditions deemed clinically significant by the investigator. The date of last prior anticancer therapy(s) and treatment response must be recorded. Pre-enrollment imaging data can be collected for the investigator's reference. A complete medication history within 28 days prior to the first administration of the study drug should be reported.

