7.4.2.2 Part B study

See Table 2 for details.

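### Section 7.3.7 puts the on-treatment FES-PET at C2D8 but Tables 1–3 put it at C2D1; Table 2 omits the Part B screening scan, and no table carries the FDG-PET, that the text requires

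*Protocol*

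**What the plan says.** Section 7.3.7 places both tracers, FES and FDG, "PET/CT at screening period and C2D8 to monitor" ER occupation and inhibition. It excludes no part of the study, and it asks that the FES and FDG scans lie within 7 days of each other.

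The section headed "7.4.1 Screening Period (Day -28~Day -1) for All Subjects" lists FES-PET/CT among the screening procedures. It does not list FDG-PET.

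The schedules read differently. The FES-PET row is marked at screening and C2D1 in Table 1 (Part A), at C2D1 only in Table 2 (Part B), and at screening and Cycle 2 Day 1 in Table 3 (Part C). The C2D1 visit window is ±3 days in all three. No table has a C2D8 column or an FDG-PET row.

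The pointers lead to different places. For PK and PD sampling the Synopsis says "Please see Section 7.5.1 PK Samples and Section 7.3.7 18F-FES PET/CT". For the Part B treatment period, Section 7.4.2.2 says "See Table 2 for details".

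The footnote to the FES row in the tables gives the purpose: "Using 18F-FES PET to monitor the detect in ER target occupation and inhibition". Section 3.4 makes the associated endpoint exploratory: "The correlation between ER target inhibition by using" FES-PET/CT and efficacy. Section 4.5 has the RP2D chosen by "pooling and evaluating all available PK, PD, target engagement, efficacy, safety, and tolerability data".

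**The concern.** Text and tables instruct sites differently on three things: the day of the on-treatment scan, whether a Part B patient has a baseline scan, and whether FDG-PET is done at all. The protocol does not say which source governs. The opening of Section 7 presents the text and the three tables as describing the same procedures, so two sites can both comply and still collect different data.

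The baseline scan matters most because it cannot be recovered: once dosing has begun, a pre-treatment image is no longer obtainable. The pharmacodynamics analysis set in Section 10.2.5 asks only for a non-baseline value, so a Part B patient without a baseline scan would still enter the set, but with no change from baseline to contribute.

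The scan day matters for the exposure analysis. Section 10.6 plans to relate exposure or dose to biomarkers, and a scan on a day without PK sampling has no same-day concentration to pair with. FES-PET is the only PD measure the protocol names; the other biomarker entry in Section 3.4 is open-ended.

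**Working it through.** There is no stated figure to reproduce, so the check sets the sources side by side and counts days.

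| Source | Screening FES | On-treatment FES | FDG |
|---|---|---|---|
| Section 7.3.7 | required, no part excluded | C2D8 | same occasions as FES |
| Section 7.4.1 | listed, all subjects | not covered | not listed |
| Table 1 (Part A) | marked | C2D1 | absent |
| Table 2 (Part B) | empty | C2D1 | absent |
| Table 3 (Part C) | marked | C2D1 | absent |

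**Can the visit window reconcile the days?** Cycles last 28 days. Counting C1D1 as day 1, and using nominal days:
- C2D1 = 28 + 1 = day 29. With ±3 days: 29 − 3 = 26 to 29 + 3 = 32.
- C2D8 = 28 + 8 = day 36.
- Gap from the scheduled day: 36 − 29 = 7 days. Gap from the end of the window: 36 − 32 = 4 days.

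The window does not reach C2D8.

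**Palbociclib phase in Part B.** Palbociclib is given on days 1–21 of each cycle and withheld on days 22–28. Nominally it is on for days 1–21, off for days 22–28, and on again from day 29. A C2D1 scan therefore follows the seven days off. A C2D8 scan on day 36 falls on the eighth day of the second dosing block (36 − 28 = 8). The two days are not equivalent for the combination.

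**PK pairing.** The sampling tables in Section 7.5.1 include C2D1 in all three parts. None includes C2D8.

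**Patients affected by the missing Table 2 mark.** Section 5.1 gives about 12 Part B patients; Section 4.2.2 gives about 24. The number without a baseline scan runs from 0, if every site follows Sections 7.3.7 and 7.4.1, to all of Part B (about 12 or about 24, depending on which size is right) if every site follows Table 2 alone.

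**Reliability of the table reading.** Positions come from tables extracted by program. The C2D1 placement rests on column position. The absence of the Part B screening mark rests also on a count: the row has one mark in Table 2 and two in each of Tables 1 and 3.

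**The case against.** A reader might infer that change in ER occupancy cannot be computed in Part B at all, or that the Part B scans are unusable. The documents do not support that. Section 7.3.7 requires the screening scan without excepting Part B, Section 7.4.1 lists it for all subjects, and the Synopsis sends PD readers to Section 7.3.7. The reference to Table 2 in Section 7.4.2.2 sits under the treatment period, so a site working through the sections in order would meet the screening scan first. One table cell disagrees with the text, and the change is lost only where that table alone is followed. Nor does the protocol define ER inhibition as change from baseline, so an unpaired scan is much weaker without being formally useless. This objection stands, and it limits the point to a contradiction.

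A reader might also infer that seven more days of dosing would shift occupancy through accumulation of FWD1802. The only evidence in the protocol, Section 1.2.2, reports no marked accumulation in rats and dogs. That is nonclinical, but it gives no support to the inference. PK pairing and palbociclib phase are the sounder reasons to fix the day.

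The 7-day spacing between tracers might be offered as a reconciliation, with FES at C2D1 and FDG at C2D8. Section 7.3.7 places both scans at C2D8, and no table holds an FDG scan on any day, so this reading is not written down anywhere.

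Finally, the link to dose selection is modest. Target engagement is one of several pooled inputs in Section 4.5; Parts A and C, which inform the monotherapy dose, have the screening mark; and the endpoint in Section 3.4 is exploratory. This also stands, although the Synopsis has the SMC use PD data in judging the Part B combination dose.

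**Conclusion.** The point holds as an internal contradiction with three parts: C2D8 against C2D1 for the on-treatment scan, a screening FES-PET required by the text but missing from Table 2, and FDG-PET required by Section 7.3.7 but scheduled nowhere.

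The on-treatment day differs by 7 nominal days in every part, 4 of them beyond the visit window. The loss of change-from-baseline values is confined to Part B and is conditional on sites following Table 2 alone. The protocol does not allow the added variability from mixed scan days to be quantified, and no figure is claimed for it.

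The consequence falls on an exploratory PD endpoint that is also one of several inputs to dose selection. It is worth correcting because a missed pre-dose scan is irrecoverable and the correction is cheap. The conclusion assumes that the extracted tables keep their column positions and that cycles start on their nominal days.

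**What to change.** Reconcile Section 7.3.7 and Tables 1–3 to a single on-treatment FES-PET day. In choosing it, note that PK is sampled on C2D1 in all parts and not on C2D8, and that in Part B the two days lie in different palbociclib phases. If a day outside the present visit columns is kept, the tables need a visit for it.

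Mark the screening FES-PET in Table 2 so that it agrees with Sections 7.3.7 and 7.4.1.

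Make Sections 7.3.7 and 7.4.1 and the tables agree on FDG-PET, either by scheduling it or by removing it from Section 7.3.7.

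The cost is a text and table correction. The Part B baseline scan adds no procedure, since the text already requires it. To be useful, the correction has to reach sites before Part B patients start dosing.

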7.4 Study Procedures

After signing the informed consent form, the subjects will complete the screening and baseline assessment during the screening period and be enrolled in the study after confirming that they meet the inclusion criteria. The investigator selects subjects who will understand the study and comply with the instructions. At each visit, the investigator shall remind subjects to follow the study protocol procedures. If the subjects withdraw from the study or terminate the treatment for any reason, they should return to the hospital for EOT visit and follow-up visits during the follow-up period. Blood samples should be collected after discontinuing the drugs and safety-related follow-up should be conducted (SFU visit).

7.4.1 Screening Period (Day -28~Day -1) for All Subjects

After signing the ICF, a subject should undergo medical screening to assess whether he/she is eligible to participate in the study according to the inclusion criteria. The screening evaluation will be completed within 28 days prior to the first administration of the investigational drug.

Administrative Procedures:

- Informed Consent
- Inclusion/Exclusion Criteria
- Demographics
- Medical history
- Concurrent diseases

Clinical Procedures/Assessments:

- Weight
- Body height
- Physical examination
- vital signs

- ECOG Score
- 12-lead ECG
- Echocardiogram

Laboratory tests:

- Blood Chemistry
- Hematology
- Coagulation
- Urinalysis
- Virology: HBV, HCV, and HIV
- Pregnancy
- COVID-19

Efficacy Assessments:

- Tumor Assessment

Biomarker Exploration:

- ¹⁸F-FES PET/CT15

Other:

- Adverse events and concomitant medication;

The information above should be obtained from the source file. For test values outside the normal range (outliers), the investigator will assess whether to repeat the test.

The investigator will review patient's medical history at the time of screening period. The history includes all current active diseases and any other conditions deemed clinically significant by the investigator. The date of last prior anticancer therapy(s) and treatment response must be recorded. Pre-enrollment imaging data can be collected for the investigator's reference. A complete medication history within 28 days prior to the first administration of the study drug should be reported.

7.4.2 Treatment Period

7.4.2.1 Part A study

See Table 1 for details.

7.4.2.2 Part B study

See Table 2 for details.

7.4.2.3 Part C study

See Table 3 for details.

7.4.3 Post Treatment Follow-up Visit

7.4.3.1 End of treatment (EOT) visit

The end-of-treatment (EOT) will occur at the earliest day possible within 7 days after the last dose of FWD1802 or the subject decides to withdraw from study treatment for any reason.

Clinical Procedures/Assessments:

- Weight
- Body height
- Physical examination
- vital signs
- ECOG Score
- 12-lead ECG
- Echocardiogram;

Laboratory tests:

- Blood Chemistry
- Hematology
- Coagulation
- Urinalysis

Other:

- Adverse events and concomitant medication;

7.4.3.2 Safety follow-up (SFU)

Mandatory safety follow-up (SFU) should be performed at 28 ± 7 days after the last administration and prior to the initiation of a new anti-tumor therapy. Subjects who

discontinue the study due to an unacceptable adverse event should be followed until AE relieves to grade 0-1 or AE is stable. If EOT visit is within the safety follow-up window, no further safety follow-up is required.

Adverse events and concomitant medication;

